## **4. Statistical Principles**

### **4.1. Confidence intervals and P-values**

The primary analysis for Trial I and Trial II will be conducted with a two-sided alpha of 0.05/2 = 0.025 to account for the two primary comparisons of interest (*oral valganciclovir* vs. *topical ganciclovir 2%*, *oral valganciclovir* vs. placebo). We will report 95% confidence intervals for the estimated differences between groups, on an absolute scale.

We will use a single-step, max-T approach to estimate p-values adjusted for multiple comparisons in each analysis. Alongside unadjusted p-values and 95% confidence intervals, we will present max-T adjusted p-values and simultaneous 95% confidence intervals for differences that account for multiple comparisons.

We will employ a multiple testing hierarchical approach in the following manner:

1. Primary endpointss (alpha = 0.025 each trial)
  - a. Trial I: viral load comparison
  - b. Trial II: Number of recurrences comparison
2. Key secondary endpoints (alpha = 0.025 shared):
  - a. Inflammation control
  - b. Antiviral resistance mutations

Gate-keeping procedure:

Primary endpoints must be significant before testing secondaries

Holm-Bonferroni correction within each family

Truncated testing if primary endpoint non-significant

Family-wise error rate controlled at 0.05 using:

Separate error rates for each trial

Sequential gatekeeping

Multiplicity adjustment within families

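### SAP 4.1 gives two primary alphas that conflict as worded; the SAP's own power and interim figures fit 0.05 per trial, and the resistance endpoint is powered at a level it will not be tested at

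*SAP*

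**What the plan says.** SAP 4.1 opens by setting, for both trials, a "two-sided alpha of 0.05/2 = 0.025 to account for the two primary comparisons of interest": oral versus topical and oral versus placebo. Two tests at 0.025 make 0.05 per trial.

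The hierarchy later in the same section lists "Primary endpointss (alpha = 0.025 each trial" and "Key secondary endpoints (alpha = 0.025 shared". It adds "Holm-Bonferroni correction within each family", a gate under which "Primary endpoints must be significant before testing secondaries", and the statements "Family-wise error rate controlled at 0.05 using" and "Separate error rates for each trial".

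On which p-value decides, SAP 4.1 says: "Alongside unadjusted p-values and 95% confidence intervals, we will present max-T adjusted p-values and simultaneous 95% confidence intervals". SAP 6.2 adds max-T results to the Trial I regression and a permutation p-value for Trial II. Protocol 8.2 endorses max-T for the two comparisons. None of these gives the level at which an adjusted p-value is judged.

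Elsewhere, SAP 3.3 powers both trials at 0.05/2 and the resistance endpoint at two-sided 0.05. For the interim look, SAP 3.5 gives an efficacy p-value of 0.0005 per comparison, and Protocol 8.3.1 gives 0.001.

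**The concern.** SAP 3.4 defines two primary comparisons per trial. If 0.025 is the whole trial's primary alpha, each comparison gets 0.0125 under an equal split, or about 0.013 under max-T. If 0.025 is the level per comparison, the trial's alpha is 0.05. The same number is attached to two different units within one section.

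The overall target does not settle it. Trial-level alphas of 0.025 and 0.025 add up to the stated 0.05, which supports the literal reading. Separate error rates for each trial point the other way. The scope matters: 0.025 per comparison gives a family-wise error of 0.0465 in one trial, and 1 − (1 − 0.0465)² = 0.091 over both if the trials are treated as independent.

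This is the primary success rule, and an unmasked efficacy look is planned. If the rule is chosen after results are known, the claimed error control can no longer be demonstrated.

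**Working it through.** **Inputs.** SAP 3.3, Trial I: residual SD 0.66, difference 0.50 log10, 35 per arm, t-test, 80% power. SAP 3.3, Trial II: 25% versus 65%, 28 per arm, z-test, 80% power. SAP 3.3, resistance: 5% versus 30%, 34 participants, unpaired z-test, 80% power. SAP 3.5: spending exponent 3.561. Assumption: the two test statistics in a trial have correlation 0.5 (shared oral arm, equal arm sizes).

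**1. Reproduce the stated power.**

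- Trial I: noncentrality = 0.50 / (0.66 × √(2/35)) = 3.17 on 68 df.
- Trial II: pooled SE = √(2 × 0.45 × 0.55 / 28) = 0.133; SE under the alternative = √((0.25 × 0.75 + 0.65 × 0.35) / 28) = 0.122. At 0.025 (z = 2.241), power = Φ((0.40 − 2.241 × 0.133) / 0.122) = 79.9%.

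| Level per comparison | Meaning | Trial I | Trial II (pooled / arcsine) |
|---|---|---|---|
| 0.0270 | max-T, 0.05 per trial | 81.6% | 80.8% / 81.3% |
| 0.025 | 0.05/2 | 80.8% | 79.9% / 80.4% |
| 0.0132 | max-T, 0.025 per trial | 73.2% | 71.9% / 73.3% |
| 0.0125 | 0.025/2 | 72.5% | 71.1% / 72.6% |

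Only the first two rows match the stated 80%, and both amount to 0.05 per trial. Two tests at 0.025 give a family-wise error of 0.0465; two at 0.0125 give 0.0236.

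**2. Interim p-values.** Spend = α × t^3.561, and (1/3)^3.561 = 0.0200. So α = 0.05 gives 0.0010 (the Protocol's figure), 0.025 gives 0.0005 (the SAP's per-comparison figure), and 0.0125 gives 0.00025, which appears nowhere. This check discriminates only at one-third: α = 0.0125 would reach 0.0005 at about t = 0.405, inside the permitted window.

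**3. Size if the line is literal.** The chance of an unadjusted p-value between 0.0125 and 0.025 is 80.8 − 72.5, about 8%, in Trial I. In Trial II it is 79.9 − 71.1, about 9% (pooled), or 80.4 − 72.6, about 8% (arcsine).

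**4. Size if the line is shorthand.** Three rules remain, each controlling 0.05 per trial before the interim look:

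- Unadjusted p at 0.025.
- Max-T adjusted p at 0.05, equivalent to a nominal 0.027 and worth under 1 point of power.
- Holm on a 0.05 family, with a first step at 0.025 and a second at 0.05. By simulation, power for oral versus placebo runs from about 81% to 86% in Trial I and 79% to 84% in Trial II. The gain is about 0.2 points if topical equals oral and 4 to 5 points if topical equals placebo.

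**5. Final level after the interim look.** For max-T at 0.05 with the SAP's spending function, the final family-wise level is about 0.0495 at t = 1/3, 0.0489 at 15 of 35 per arm, and 0.0483 at one-half. Subtracting the spent alpha gives 0.0490, 0.0476 and 0.0458. That is needlessly strict, because it ignores the correlation between looks.

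**6. Resistance endpoint (pooled / arcsine).** At 0.05: 78.7% / 83.2%, which reproduces the SAP. At 0.025: 69.1% / 75.1%. At 0.0125, the Holm first step over two key secondaries: 59.0% / 66.4%.

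**The case against.** The strongest reply is that the hierarchy line is loose shorthand. Both lines carry the same number, the opening sentence says why it is 0.025, and SAP 3.3 and 3.5 use 0.025 per comparison throughout. This is probably right. It means that the 8% to 9% band and the fall to 71–73% power follow only from the less likely reading.

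A reader might therefore infer from the hierarchy line that both trials are underpowered, or that error control fails. The documents do not support either. The stated power is correct for 0.05 per trial, and an unadjusted p-value judged at 0.025 is a valid rule (0.0465 per trial).

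It can also be said that the deciding p-value is implied: unadjusted at 0.025, with max-T as support. That is a natural reading, and max-T is not the only sound choice. But Holm within each family also covers the primary family, and it would give a different second step. The permutation test is a way to obtain a p-value, not a rival alpha. The gate wording is plural and may mean that both trials must succeed; the gap there is mostly missing detail.

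On resistance, SAP 3.3 itself calls the unpaired calculation conservative, and the planned analysis is paired. So 69–75% is not the power of the planned test, but the mismatch between the powered and the tested level stands.

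Protocol 8.2's 36-point Trial II difference gives 69.7% power at 0.025 and fits neither primary alpha. It is a separate discrepancy and does not support the literal reading.

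**Conclusion.** The two alpha statements conflict as worded, and the hierarchy line is most likely the wrong one. The SAP's power figures, and the interim figures of both documents at one-third information, fit 0.05 per trial.

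The size depends on intent. Read literally, the line costs about 8 to 9 points of power per comparison. Read as shorthand, the surviving rules differ by under 1 point (unadjusted versus max-T), or by up to 4 to 5 points with Holm, depending on the topical effect. The resistance endpoint's stated power does not hold at the level assigned to it.

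This should be fixed before unmasking. It is a gap in the decision rule, not evidence that the design is unsound. The figures rest on the SAP's design effects and residual SD, the 0.5 correlation between tests, and, for resistance, the SAP's unpaired test.

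**What to change.** In SAP 4.1:

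- Replace the per-trial 0.025 with a two-sided family-wise alpha of 0.05 within each trial, over oral versus placebo and oral versus topical.
- Name one deciding procedure. Max-T adjusted p-values with matching simultaneous intervals agree with Protocol 8.2 and SAP 6.2; unadjusted p at 0.025 is also valid. Limit Holm to the key secondaries, unless Holm is the procedure chosen for the primaries.
- State which comparison, in which trial, opens the gate, and how the shared 0.025 is divided, given that the resistance analysis uses samples from both trials.

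In SAP 3.5, say that the final level comes from the group-sequential spending calculation at the actual information fraction, not from subtracting the spent alpha. In SAP 3.3, restate the resistance power at the level at which it will be tested.

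If 0.05 across both trials is what is meant, keep 0.025 per trial. Then restate power as about 73% (Trial I) and 72% (Trial II), and the one-third boundary as 0.0005 per trial (0.00025 per comparison).

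The cost is wording only. The per-trial rule needs no extra participants. Under the alternative, holding 80% power in Trial I at 0.0125 per comparison would take 41 evaluable per arm instead of 35, and the detectable Trial II difference would be 43 points instead of 40.

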**Primary analysis for Trial II.** The primary outcome for Trial II is the proportion of participants experiencing CMV recurrence over 12 months. We acknowledge that hypothesizing fewer recurrences in the placebo group compared to the oral antiviral group is contradictory to what one might think would typically occur with exposure to antivirals. However, data from a previous observational study showed a one-year recurrence risk of 25.0% (3/12) among participants who did not receive antiviral treatment and 75.0% (9/12) in participants receiving systemic antiviral treatment (oral ganciclovir or valganciclovir), which is similar to the experience of other research. Additionally, it is well documented that long-term suppressive-level dosing of antiviral in an immunodeficient host or in an immunologically privileged organ (such as the eye) can create an environment permissive to the development of antiviral resistance. Given 28 participants per arm (105 total from Trial I with 20% loss to follow-up) and a recurrence risk of 25% in the placebo group, we can detect a difference of 40 percentage points between the oral valganciclovir and the placebo groups (from 25% to 65%), using a two-sample z-test for proportions with 80% power and a two-sided alpha of 0.05/2.

**For Specific Aim 3,** we estimated the minimum detectable effect for the difference in prevalence of infections that have antiviral resistance mutations among recurrent infections in Trial II among patients who receive long-term antiviral prophylaxis compared with their infections at baseline. Aim 3 will focus on patients in the two active treatment arms in Trial II, because we would expect long-term use of topical and oral antivirals to lead to similar selection for antiviral resistance. From 117 patients enrolled, we conservatively assumed that 72% of patients would complete both Trial I and Trial II (n=84). We further assumed that 60% of patients will develop a recurrent infection over the monitoring period during the trials (Table 1). Participants who receive active treatment in Trial II (treatment regimens C+D) will contribute to the Aim 3 analysis (n=34). The analysis will be a paired analysis, comparing the proportion of recurrent infections with antiviral resistance mutations with that same proportion at baseline.

Table 1. Anticipated participant enrollment, and follow-up by treatment patterns

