### **3.6. Timing of the final analysis**

The final analysis for Trial I will be conducted only after 9 days have elapsed since the treatment of the final enrollee. The final analysis for Trial II will be conducted only after 7 months have elapsed since the treatment of the final enrollee. We anticipate at least two months for data processing and resolution of potential errors, anomalies, or missing values.

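### SAP 4.1 is inconsistent on gatekeeping: read literally, Trial II can block or delay the Trial I key secondary, while other lines point to a gate within each trial

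*SAP*

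**What the plan says.** The hierarchy is in SAP 4.1. Level 1 is "Primary endpointss (alpha = 0.025 each trial"), listing Trial I viral load and Trial II recurrences. Level 2 is "Key secondary endpoints (alpha = 0.025 shared"), listing inflammation control and antiviral resistance mutations. Four rules govern these levels:

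- the gate: "Primary endpoints must be significant before testing secondaries" (plural);
- the truncation rule: "Truncated testing if primary endpoint non-significant" (singular, trial not named);
- the within-family procedure: "Holm-Bonferroni correction within each family";
- overall control of the family-wise error rate at 0.05, achieved partly by "Separate error rates for each trial".

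SAP 3.4 names two primary comparisons per trial, oral v placebo and oral v topical. SAP 4.1 does not say which of them opens the gate.

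Inflammation control corresponds to Aim 1b, the Trial I hypothesis on clinical inactivity at day 7 (SAP 2.2). The resistance endpoint compares baseline with recurrence in people who took part in both trials and received an active drug in Trial II (SAP 6.2, Aim 3).

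On timing, SAP 3.6 states: "The final analysis for Trial I will be conducted only after 9 days have elapsed since the treatment of the final enrollee". The Trial II primary runs over 12 months (SAP 6.1).

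**The concern.** The plural gate and the single shared family join two separate randomisations. Followed as written, they mean that a clear Trial I effect on inflammation could not be declared if prophylaxis made no difference in Trial II. They also mean that the test could not be made at Trial I's final analysis, because the Trial II primary would not yet exist. Resistance would likewise go untested whenever Trial I was null.

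The lines on separate error rates and on a single primary endpoint suggest that something else was intended. The rules cannot all be followed together. If the text stays as it is, the choice of reading could be made after results are known.

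**Working it through.** **1. The plan's own figures.**
- Trial I (SAP 3.3): residual SD = 0.98 × √(1 − 0.74²) = 0.659, stated as 0.66. With a difference of 0.50, 35 per arm and two-sided alpha 0.025, t-test power is 0.808. The normal approximation gives a shift of 0.50 / (0.66 × √(2/35)) = 3.169 and power Φ(3.169 − 2.241) = 0.823. The SAP states 80%.
- Trial II (SAP 3.3): 25% v 65%, 28 per arm, alpha 0.025 gives power 0.799. The SAP states 80%.
- Error rate (SAP 4.1): 0.025 + 0.025 = 0.05 reproduces the stated 0.05, if 0.025 is each trial's whole primary alpha.

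**2. Hand check of the joint gate, counting one primary per trial.** With independent trials at 80% power, the gate opens with probability 0.80 × 0.80 = 0.64. If Trial II is null, it is 0.80 × 0.025 = 0.02. A Trial I-only gate gives 0.80.

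**3. Simulation with two contrasts per trial** (400,000 draws, critical value 2.241, that is 0.025 per contrast). Trial I uses normal contrasts sharing the oral arm (correlation 0.5), with 0.50 log10 on both. Trial II uses binomial counts and a pooled z-test, placebo 25% and oral 65%. The topical risk is an assumption, since the SAP gives none. The trials are taken as independent.

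Trial I alone: each contrast 0.82, at least one 0.927, both 0.719.

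| Trial II scenario | At least one Trial II contrast | Both Trial II contrasts | Gate: any one per trial | Gate: all four | Gate: oral v placebo in both trials |
|---|---|---|---|---|---|
| Topical 65% | 0.799 | 0.0155 | 74% | 1.1% | 65% |
| Topical 45% | 0.802 | 0.208 | 74% | 15% | 65% |
| Topical 25% | 0.905 | 0.677 | 84% | 49% | 65% |
| Null: 25% in every arm | 0.044 | 0.0037 | 4% | 0.3% | 2% |

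Gate probabilities are products across trials. For example, 0.927 × 0.799 = 0.74, and 0.719 × 0.0155 = 0.011. Oral v placebo in both is 0.823 × 0.791 = 0.65, or 0.823 × 0.024 = 0.02 under the null.

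With a null Trial II and the most lenient joint reading, a Trial I that succeeded on at least one contrast loses its key secondary in 1 − 0.044 = about 96% of cases.

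**4. The Holm step.** With two endpoints at 0.025 the steps are 0.0125 and 0.025. An inflammation p-value of 0.0125 or less is rejected whatever the resistance result, and one above 0.025 always fails. Resistance decides only in between. If inflammation control had 80% power at 0.025 (assumed; the SAP gives none), the shift is 2.241 + 0.842 = 3.083. Then P(p ≤ 0.0125) = Φ(3.083 − 2.498) = 0.72, so the in-between zone holds about 0.80 − 0.72 = 8%. The same formula gives about 10% at 50% power and 5% at 90%.

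**5. Error rate under a per-trial gate.** Where 0.025 is each trial's whole primary alpha, and each trial's secondary is tested at 0.025 after its own primary, simulation (2,000,000 draws, independent p-values) gave a maximum family-wise error of 0.0495. If 0.025 is per contrast, as the opening of SAP 4.1 and the sample-size text have it, each trial can spend 2 × 0.025 = 0.05. Both together can spend 4 × 0.025 = 0.10 (1 − 0.975⁴ = 0.096 if independent).

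**The case against.** The strongest reply is that the joint gate is only one reading. "Separate error rates for each trial" and the singular wording of the truncation rule fit a gate within each trial. This stands: the defect is a contradictory rule, and a reader who infers that the SAP definitely requires both trials to succeed goes further than the text.

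Further limits also stand:

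- A reader might take 1% as the size of the problem. It needs the strictest reading and a topical risk of 65%. The statement "we would expect long-term use of topical and oral antivirals to lead to similar selection for antiviral resistance" concerns resistance, not recurrence, so it does not support that risk.
- A reader might infer that Holm always needs the resistance p-value. It does so only between 0.0125 and 0.025.
- Trial II is not unrelated to Trial I. It re-randomises Trial I participants, with some direct entrants (SAP 2.1). Resistance is not independent of Trial II either, since its sample is Trial II recurrences on active drug.
- SAP 6.1 describes the clinical-inactivity analysis as exploratory and supplementary, and SAP 6.2 reports it by arm with max-T intervals and no gate. The estimate would be published either way; only the confirmatory claim is at stake.
- The joint gate adds no false positives and leaves both primary analyses untouched.

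These points lower the severity. They do not settle which rule applies. The status given in SAP 6.1 is itself at odds with listing inflammation control as an alpha-controlled key secondary in SAP 4.1.

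**Conclusion.** The point holds as an internal inconsistency with a material consequence under the literal reading. A joint gate opens in about 1% to 84% of trials at the design effects, depending on the reading and the topical risk assumed. The figure is 65% if oral v placebo must succeed in both trials. If Trial II is null, it opens in 0.3% to 4%. A single-contrast Trial I gate opens in about 82%. The Holm dependence is a smaller, secondary effect.

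These figures assume 0.025 per contrast, independent trials, equal Trial I effects on both contrasts, and simple z-tests in place of the max-T and permutation procedures. The null Trial II result does not depend on a guess at the topical effect.

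Severity: should be fixed. The primary analyses are unaffected and the joint gate is conservative.

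**What to change.** Rewrite the hierarchy in SAP 4.1 by trial and by contrast, before any unmasked comparison is seen:

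- **Trial I:** test inflammation control for a contrast only after that same contrast is significant on viral load, at that contrast's alpha, at the Trial I final analysis. This fixed sequence spends no alpha beyond the primary tests.
- **Resistance:** either gate it on the Trial II primary comparison of oral v placebo, at that contrast's alpha, or report it as an estimate with a confidence interval. SAP 6.2 already calls this analysis observational.
- **Shared alpha:** delete the shared 0.025 and the Holm step across the two trials' endpoints.
- **Meaning of 0.025:** state whether it is per contrast or per trial. If per contrast, the 0.05 claim holds only within each trial and should say so.
- **Status of inflammation control:** reconcile SAP 4.1 with SAP 6.1. If it is exploratory, remove it from the hierarchy. If it is a key secondary, amend SAP 6.1.

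The cost is SAP wording only, with no added patients, visits or data. Under the per-contrast reading the two trials together may spend up to 0.10, which should be accepted openly or avoided by adopting 0.025 per trial.

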## 4.2. Protocol deviations

The primary analyses will be conducted on an intent-to-treat basis. Individuals who receive the mandated dose of the medication to which they have been randomized are assumed adherent.

Adherence will be assessed via a study calendar patients use to report adherence and objectively by pill counting and weighing of medication bottles. The details of the assessments are included in the Protocol. Participants who miss a scheduled dose of medication will be instructed to continue with their next scheduled dose of tablets or eye drops.

In the event an individual receives a medication to which they were not randomized, a protocol deviation will be reported. A per protocol analysis will be conducted using only individuals who were adherent (an analysis to be sharply distinguished from the primary intent-to-treat analysis).

Any individual who receives even one dose of study medication or placebo is included in the safety analysis population. Any individual who receives study medication and who has a follow-up visit during the prescribed period is included in the complete case analysis.

